4.2. Secondary Objectives and Endpoints

Secondary objectives will aim at evaluating the difference in time in range, quality of life and treatment satisfaction.

4.2.1. TIR change over time

- Objective: To assess the change overtime of the TIR collected at baseline and every three months until 12 months.
- Endpoint: The Time In Range (TIR) defined as the proportion of sensor glucose concentration within the target range of 70-180 mg/dL (3.9–10.0 mmol/L) every 3 months.

4.2.2. Satisfaction score based on the DTSQc

- Objective: To evaluate satisfaction score based on the DTSQc evaluated at 6 months.
- Endpoint: The different DTSQc versions will be used to assess satisfaction in the following populations:
 - DTSQc Adult (≥ 18 years old)
 - DTSQc Teenager (13-17 years old)
 - DTSQc Parent (7-12 years old)

4.2.3. Quality of life based on DQoL

- Objective: To evaluate the change from baseline in quality of life based on the DQoL evaluated at 6 and 12 months.
- Endpoint: the DQoL questionnaire will be used and the mean scores will be compared between baseline and 6 and 12 months. The different DQoL versions will be used to assess quality of life in the following populations:

- DQoL Adult (≥ 18 years old)
- DQoL Adult with Adolescent-oriented items (13-17 years old)

No DQoL version and therefore no collection for patients 7-12 years old

4.2.4. Fear of hypoglycemic events based on the Hypoglycemia Fear Survey (HFS)

- Objective: To evaluate the change from baseline in the fear of hypoglycemic events based on the HFS evaluated at 6 and 12 months.
- Endpoint: the HFS questionnaire will be used and the mean scores will be compared between baseline and 6 and 12 months. The different HFS versions will be used to assess the fear of hypoglycemic events in the following populations:
 - HFS Adult (≥ 18 years old)
 - HFS Teenager (13-17 years old)
 - HFS Parent (7-12 years old)

4.2.5. Glycemic parameters

- Objective: To evaluate the change of glycemic parameters at baseline and every three months until 12 months and the change in HbA1c from baseline to 6 and 12 months.
- Endpoint: the mean time of sensor glucose values below 70mg/dL and below 54mg/dL, the time of sensor glucose value above 180mg/dL and above 250mg/dL at baseline and every 3 months. The change in HbA1c from baseline to 6 and 12 months follow up.

4.2.6. Satisfaction score on the DTSQs

- Objective: To evaluate the treatment satisfaction score on the DTSQs evaluated at baseline, 6 and 12 months.
- Endpoint: The different DTSQs versions will be used to assess satisfaction in the following populations:
 - DTSQs Adult (≥ 18 years old)
 - DTSQs Teen (13-17 years old)
 - DTSQs Parent (7-12 years old)

5. Investigation Plan

This study is a local, post-market, non-interventional, prospective, single-arm, multi-center, non-randomized study assessing the glycemic control effect, treatment satisfaction and the quality of

life of patients using MiniMed™ 780G System as per the standard care of practice. This study has a single-arm design which will recruit a maximum of 306 subjects in up to 32 sites in France. At the time of Clinical Investigational Plan finalization, the list of participating sites was not finalized. The complete list, which includes the name, position and address of the investigators responsible for conducting the study, will be available under separate cover and provided to the sites.

[figure not shown]
To avoid introduction of bias to the study results due to disproportionate enrollment, enrollment at any individual site shall not exceed 10% (30 subjects) of the total sample size. It is expected that sites enroll a minimum of 10 subjects per site.

Subject enrolled in this study (or his/her parent/legal representative in case of DTSQ and HFS for patients 7-12 years old) will be asked to complete the questionnaires DTSQ, DQoL (if patient is ≥ 13 years old) and HFS at baseline/enrollment visit and at 6- and 12- month follow-up visits.

The following measures are taken to minimize potential sources of bias:

- A multi-center design is used to ensure a representative sample of physicians providing the treatment and to reach a reasonable enrollment period.
- Site selection will be done per predefined selection criteria.
- Only physicians that have adequate documented experience in diabetes management will participate.
- Site training is performed according to the training & education plan set up for the pump use in order to assure full understanding and engagement to comply with the pump best utilization.
- Consecutive screening and enrollment will be encouraged and enforced as much as possible.

Figure 1: Study design overview

CareLink data uploads from the devices should be done as per clinical practice, i.e. once a week. CareLink data evaluation will be done every 3 months.

An overview of data collection is given in the Table 1.

Table 1: Schedule of assessments

Data collection	Enrollment /Baseline	6-month Follow-up (±45 days)	12-month Follow-up (±45 days)
Data Release Form	✓		
Inclusion and exclusion criteria	✓		
Demographics	✓		
Medical history	✓		
HbA1c¹	✓	✓	✓
Auto Mode Activation Date	✓		
Ensure that CareLink™ Personal upload was done²	✓ ⁴	✓	✓
CGM data	✓	✓	✓
Study Exit			✓
Study Deviation	Upon occurrence		
QUESTIONNAIRES :			
DTSQs	✓	✓	✓
DTSQc		✓	
DQoL³	✓	✓	✓
HFS	✓	✓	✓

1. Available HbA1c value collected up to 30 days before enrollment and more or less 30 days from 6-month and 12-month follow up visits can be used.
2. CareLink™ data should be uploaded via Bluetooth connectivity from the devices or via USB connection as per clinical practice, i.e. once a week. CareLink™ Data evaluation will be done every 3 months for secondary objectives.
3. DQoL will not be administered in case patient is between 7 and 12 years old.
4. Baseline CGM data will be collected before Auto Mode activation at the end of the run-in phase

6. Determination of Sample Size

The sample size was determined using a one sample paired test assuming a one-sided type I error rate of 0.05 and a power of 90%. The TIR at baseline is assumed to be 60% and the TIR at 6 months follow up (TIR calculated using overall 6 months CGM data) is assumed to be 63% with same standard deviation as 14% and a correlation as 0.5. Thus, the hypothesis to be tested is:

$$H_0: \mu_{TIR6m} - \mu_{TIR \text{ baseline}} = d_0$$

$$H_A: \mu_{TIR6m} - \mu_{TIR \text{ baseline}} > d_0$$

where $d_0 = 3$ is the expected increase of TIR at 6 months. The sample size needed to demonstrate this hypothesis is 245 paired assessments per subject. The calculation is adjusted for loss-to-follow-up and protocol failures, including potential subjects with less than 70% of the time in Auto Mode and with an assumption considering an attrition rate of 20%. The total number of subjects to be enrolled is 306.

[figure not shown]
7. Statistical Methods

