Statistics	
The sample size was determined using a one sample paired test assuming a one- sided type I error rate of 0.05 and power greater than 90%. The TIR at baseline is assumed to be around 60% and the TIR at 6 months follow up is assumed to be 63% with standard deviation as 16% and a correlation as 0.5. The sample size needed to demonstrate this hypothesis including 20% of attrition rate is 306.
 
Descriptive statistics will be used to summarize patient characteristics. For categorical variables, the description will consist in frequency and the percentage of each category. For continuous variables, the description will consist summary statistics as mean, standard deviation, standard error, minimum, median and maximum.
 
The primary endpoint on efficacy defined as the change of TIR at 6 months from Auto Mode activation will be analyzed by means of paired (samples) t-test or Wilcoxon signed rank sum test according to the normal or non-normal distribution.
 
The primary outcome will include all patients as the ITT population. Sensitivity analysis will include the per protocol patients as defined by >70% Auto Mode usage.

4. Introduction

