- f) Secondary Endpoint #6: The different DTSQs versions will be used to assess satisfaction in the following populations:
 - a. DTSQs Adult (≥ 18 years old)
 - b. DTSQs Teen (13-17 years old)
 - c. DTSQs Parent (7-12 years old)

6. Study Design

This study is a local, post-market, non-interventional, prospective, single-arm, multi-center, non-randomized study assessing the glycemic control effect, treatment satisfaction and the quality of life of patients using MiniMed™ 780G System as per the standard care of practice. This study has a single-arm design which will recruit a maximum of 300 subjects in up to 32 sites in France. At the time of Clinical Investigational Plan finalization, the list of participating sites was not finalized. The complete list, which includes the name, position, address and contact details of the investigators responsible for conducting the study for each investigational site, will be available under separate cover and provided to the sites.

To avoid introduction of bias to the study results due to disproportionate enrollment, enrollment at any individual site should not exceed 10% (30 subjects) of the total sample size. It's expected that sites enroll a minimum of 10 subjects per site.

Enrollment will be competitive across study sites. The per-study site enrollment cap may be increased upon Sponsor approval.

[figure not shown]
Subject enrolled in this study (or his/her parent/legal representative in case of DTSQ and HFS for patients 7-12 years old) will be asked to complete the questionnaires DTSQ, DQOL (if patient is ≥ 13 years old) and HFS at baseline/enrollment visit and at 6- and 12- month follow-up visits.

The following measures are taken to minimize potential sources of bias:

- A multi-center design is used to ensure a representative sample of physicians providing the

- treatment and to reach a reasonable enrollment period.
- Site selection will be done per predefined selection criteria.
 - Only physicians that have adequate documented experience in diabetes management will participate.
 - Site training is performed according the training & education plan set up for the pump use in order to assure full understanding and engagement to comply with the pump best utilization.
 - Consecutive screening and enrollment will be encouraged and enforced as much as possible.

Figure 1: Study design overview

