12.1. Sample size justification

The primary endpoint is to evaluate if the MiniMed™ 780G therapy in Auto Mode increases the proportion of Time In Range (TIR) at 6 months compared to the MiniMed™ 780G therapy in manual mode at baseline. The endpoint is the Time In Range (TIR) defined as the proportion of sensor glucose concentration within the target range 70-180 mg/dL (3.9-10.0 mmol/L).

The Pivotal study [12, 13] enrolled adolescents (ages 14–21 years) and adults (ages 22–75 years) with type 1 diabetes in a multicenter pivotal trial. The Medtronic MiniMed™ 670G system was used during a 2- week run-in phase without HCL control, or Auto Mode, enabled (Manual Mode) and, thereafter, with Auto Mode enabled during a 3-month study phase. The study has shown a significant

improvement on TIR of 60.4% (10.9%) to 67.2% (8.2%) in adolescents and from 68.8% (11.9%) to 73.8% (8.4%) in adults. Using this information and considering that this study is expected to include around 32 sites and including also patients aged >7 years old, a lower increase of TIR and higher variability are expected. The following assumptions were made:

- Improvement in TIR of at least 3% points at 6 months compared to the baseline.
- Standard deviation as 16% due to the mixed population and multiple sites expected for this study.

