12.2. Sample size Calculations

The sample size was determined using a one sample paired test assuming a one-sided type I error rate of 0.05 and a power greater than 90%. The TIR at baseline is assumed to be 60% and the TIR at 6 months follow up (TIR calculated using overall 6 months CGM data) is assumed to be 63% with same standard deviation as 16% and a correlation as 0.5. Thus, the hypothesis to be tested is:

$$H_0: \mu\text{TIR6m} - \mu\text{TIR baseline} = d_0$$

$$H_A: \mu\text{TIR6m} - \mu\text{TIR baseline} > d_0$$

where $d_0 = 3$ is the expected increase of TIR at 6 months. The sample size needed to demonstrate this hypothesis is 245 paired assessments per subject. The calculation is adjusted for loss-to-follow-up and protocol failures, including potential subjects with less than 70% of the time in Auto Mode with an assumption considering an attrition rate of 20%. The total number of subjects to be enrolled is 306.

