7.12. Changes to Planned Analysis

The analysis described in the CIP could differ from that presented in this SAP due to data availability. Any deviation from the original statistical plan will be described and justified in the final report, as appropriate.

8. Validation Requirements

All collected data will be reviewed for completeness, correctness and consistency. In case of issues, queries will be sent to the investigator to complete, correct or comment the data. To ensure the quality of the results provided for the study in the form of tables, listings and figures, and the derived datasets the following processes are used:

- Statistical programming and analysis will be done by qualified programmer(s) and statistician(s) following applicable procedures and best practices.
- The derived datasets and tables will be validated by a second programmer or statistician.
- Statistical results will be reviewed and confirmed by a second statistician.

The complete set of Tables, Listings, and Figures (TLF) will be 100% checked for accuracy, completeness, and consistency prior to inclusion in the interim or final clinical study report. According to Medtronic SOPs the level I validation (double programming) will be implemented for primary and secondary endpoints, while level II validation (the peer reviewer reviews the code; where appropriate, performs manual calculations or simple programming checks to verify the output) will be implemented for all other outputs.

9. References

1. <http://www.strobe-statement.org/index.php?id=available-checklists>

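### SAP section 6 pairs an SD of 14% with 90% power, 245 pairs and 306 enrolled, but those totals follow from the protocol's SD of 16%

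*SAP*

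**What the plan says.** SAP section 6 describes a paired test with one-sided alpha 0.05 and power 90%. Mean TIR is assumed to rise from 60% to 63%, "with same standard deviation as 14% and a correlation as 0.5". It concludes: "The sample size needed to demonstrate this hypothesis is 245 paired assessments per subject". With 20% attrition it sets enrolment at 306.

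The protocol has the same means, correlation, alpha, attrition and totals, but a different SD:

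- Synopsis, Statistics: TIR at 6 months "is assumed to be 63% with standard deviation as 16% and a correlation as 0.5".
- Section 12.1, with the reason: "Standard deviation as 16% due to the mixed population and multiple sites expected for this study".
- Section 12.2: "with same standard deviation as 16% and a correlation as 0.5", again leading to 245 pairs and 306 enrolled. Power is described there as greater than 90%, not as 90%.

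The SAP gives no reason for 14%. Its section 7.12 says only, in general terms: "The analysis described in the CIP could differ from that presented in this SAP due to data availability".

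The enrolment ceiling also differs. Protocol section 6 describes a design "which will recruit a maximum of 300 subjects in up to 32 sites in France", while SAP section 5 sets the maximum at 306 and protocol 12.2 requires 306. The protocol synopsis says approximately 300.

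**The concern.** A lower SD with the same effect, correlation, alpha and power must give a smaller sample size. The SAP lowers the SD from 16% to 14% and keeps 245 and 306 unchanged, so at least one figure in its section 6 does not belong with the others. The conflict lies inside that section and does not depend on which protocol version the SAP was written against.

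What is at stake is traceability. Protocol 14.7.4 commits the sponsor to sending the SAP to the French health authority (HAS) before the analyses are run, and a reader who repeats the section 6 calculation will get 188 pairs, not 245. Two documents would also give two different planning SDs against which to read the observed variability. The 300 versus 306 discrepancy belongs here because the margin over 245 pairs depends on how many subjects may be enrolled.

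**Working it through.** **Inputs (SAP section 6; protocol 12.2 for the alternative SD).** One-sided alpha 0.05; power 0.90; true gain 63 − 60 = 3 points; correlation 0.5; SD 14 (SAP) or 16 (protocol); attrition 20%. The null difference is taken as 0. Both documents write the null as d0 = 3, but with a true gain of 3 that null gives power equal to alpha, 5%, at any sample size, so it cannot be the null that was used. That is a separate defect.

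**SD of the paired difference.** SDd = SD × √(2(1 − 0.5)) = SD, so 14 or 16.

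**Formulas.** Normal approximation: n = (SDd × (1.645 + 1.282)/3)². Exact: the smallest n at which the noncentral t power with n − 1 degrees of freedom and noncentrality (3/SDd)√n reaches 0.90. Enrolled = n/0.8.

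**Reproducing the stated totals with the protocol's SD of 16.**
- Normal approximation: 243.6, so 244.
- Exact paired t: 244 pairs give 0.8990 and 245 give 0.9000, so 245.
- Enrolment: 245/0.8 = 306.25, stated as 306. Rounding up would give 307, which is trivial.

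**The same calculation with the SAP's SD of 14.**
- Normal approximation: 186.5, so 187.
- Exact paired t: 187 pairs give 0.8988 and 188 give 0.9002, so 188.
- Enrolment: 188/0.8 = 235.
- Power at 245 pairs: 0.9554.
- Gap: 245 − 188 = 57 pairs, and 57/245 = 23%.

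**Working backwards.** For 245 pairs to give exactly 90% power, SDd must be 16.00. With SD 14 that needs a correlation of 1 − 16.00²/(2 × 14²) = 0.347, not 0.5.

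**Could another reading rescue SD 14?**

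| Variant with SD 14 | Pairs |
|---|---|
| Wilcoxon, efficiency 3/π | 188/0.955 ≈ 197 |
| Wilcoxon, worst case 0.864 | 188/0.864 ≈ 218 |
| Two-sided 0.05, 90% power | 231 |
| One-sided 0.05, 95% power | 238 |
| Two-sided 0.05, 90% power, plus Wilcoxon 3/π | ≈ 242 |

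The two Wilcoxon rows at one-sided 0.05 keep the stated alpha and power and stay well short of 245. The other three change a stated input, and none gives 245.

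**Enrolment capped at 300 (SD 16).**

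| Loss of paired data | Pairs | Power |
|---|---|---|
| 15% | 255 | 91.0% |
| 18.3% (55 of 300) | 245 | 90.0% |
| 20% | 240 | 89.5% |

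Only the 20% loss is stated in the documents; the other rows show the range.

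**The case against.** The strongest counter-argument is that nothing of substance is lost. The totals of 245 and 306 agree between protocol 12.2 and SAP section 6, they give at least 90% power under either SD, and the planning SD enters no analysis. All of that is true, and it limits the point to documentation.

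It can also be said that no passage states which SD was intended. The arithmetic shows that the SD, power and sample size do not fit together; it does not prove that the SD is the wrong item. That stands as a caution, although the protocol's three statements of 16%, its stated reason, and the exact match to 245 make a carry-over from the protocol the likeliest explanation. Under the protocol's wording of power greater than 90%, 95.5% would not contradict the power statement. But the SAP says 90%, and 245 would still not be the number needed.

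The silence of SAP 7.12 is weak evidence, because that section concerns analyses and a planning SD is not an analysis.

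On the ceiling, the synopsis's approximate 300 is harmless; only the stated maximum in protocol section 6 conflicts. Even there, the 20% allowance also covers subjects with under 70% Auto Mode use. Those subjects stay in the ITT set used for the primary analysis and contribute a pair if they have run-in and 6-month data, so the loss from that analysis may well be below 20%.

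**Conclusion.** The concern holds. With SAP section 6 as written, 90% power needs 188 pairs and 235 enrolled, against the stated 245 and 306; equivalently, 245 pairs gives 95.5% power. The protocol's SD of 16% reproduces 245 and 306 at 90.0% power. These results assume a paired t-test, a null difference of 0, a true gain of 3 points and a correlation of 0.5.

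The error does not leave the trial underpowered and alters no analysis. It should be fixed because a stated input, as written, cannot yield the stated sample size. The 300 versus 306 ceiling is a smaller inconsistency: at 300 enrolled and SD 16%, power falls below 90%, to 89.5%, only if the full 20% is lost from the primary analysis, and it holds at 90% with up to 55 losses.

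**What to change.** 1. In SAP section 6, restore SD 16%. If 14% is intended, give the reason and restate power as 95.5% at 245 pairs.
2. State in that section that the calculation tests a null difference of 0, with 3 points as the assumed true gain.
3. Use one enrolment maximum in the protocol and SAP. If 300 stands, state that power is about 89.5% (240 pairs) only if all 20% are lost from the primary ITT analysis, and that 90% holds if loss of paired data is at most about 18% (55 of 300).

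The cost is one corrected number, a sentence on the null and one aligned enrolment figure. No subjects beyond the 306 already stated are needed, and no analysis changes.

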7.1. Study Subjects

7.1.1. Disposition of Subjects

Disposition of subjects will be reported following the STROBE Statement Checklist. Number of individuals at each stage of study (number of total assessed for eligibility, number enrolled, number analyzed and number with 6-12 months follow-up) will be reported. Reasons for not participation at each stage will be reported where known.

Figure 1 – Flow diagram of Patient Disposition

7.1.2. Clinical Investigation Plan (CIP) Deviations

All deviations will be collected in the case report form, with the type of the deviation and the reason for the deviation. All deviations will be reported in Tables and Listings.

7.1.3. Analysis Sets

The following subject sets will be used for the analysis:

- The Intention To Treat (ITT) includes all patients enrolled in the study with signed Data Release Form, fulfill the inclusion and exclusion criteria. The ITT will be used for all endpoints and safety evaluation.
- The Per Protocol (PP) includes all patients enrolled in the study with signed Data Release Form, fulfill the inclusion and exclusion criteria and having at least 70% of time using the Auto Mode during the 6-month follow up. The PP set will be used for all endpoints.

The primary analysis will be performed on the ITT set. As sensitivity analysis the PP set will be used. The following table shows how each population set will be used for analyses:

Population set	Baseline assessment	Primary Endpoint	Secondary Endpoints	Adverse Events
PP	✓	✓*	✓	
ITT	✓	✓	✓	✓

* The primary endpoint on the PP population will be considered as sensitivity analysis

For patients who dropout, the analyses will include all data up to the point of their last data collection.

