9.2. Subject Enrollment

The point of enrollment is defined as the time at which the in- and exclusion criteria have been checked and fulfilled and at which the subject (or his/her parent/legal representative) and the principal investigator or authorized designee, as required, have personally signed and dated the Data Release Form (DRF). At that point, the subject is considered enrolled in the study. A study subjects ID number will be assigned, and the subject must be followed until study closure or study exit, whichever occurs first. The investigator will record on the medical file of the subject that he/she participates in this study.

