9.4. Exclusion Criteria

- Subject has MiniMed™ 780G System IFU contraindication(s).
- Subject used Predictive Low-Glucose Management (PLGM) System (i.e. MiniMed™ 640G with SmartGuard) in the 6 months before the enrolment.
- Subject used Low Glucose suspend (LGS) feature (i.e. MiniMed™ Paradigm Veo Pump) in the 6 months before the enrolment.
- Subject under Multiple-Daily Injections (MDI) treatment in the 6 months before the enrolment.
- Subject has any unresolved adverse skin condition in the area of sensor placement (e.g., psoriasis, dermatitis herpetiformis, rash, Staphylococcus infection).

10. Study Procedures

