10.8. Assessment of Safety

This is a non-interventional study assessing the glycemic control and Quality of Life of subjects with T1D. No Adverse Events or Device Deficiencies are collected, and there are no specific safety parameters to be assessed as part of the study. Complaint reporting will be done as per local requirements and Medtronic processes, including vigilance reporting for commercially approved products.

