10.10. Deviation Handling

A CIP and/or study deviation is an event where the investigator or site personnel did not conduct the clinical study according to the Clinical Investigational Plan or Clinical Investigation Agreement.

Example of deviations may include but are not limited to:

- Failure to obtain Data Release Form prior to participation in the study;
- Incorrect version of Data Release form provided to subject;
- Failure to obtain EC approval before the start of the study;
- Subject did not meet enrollment criteria and was enrolled;
- Subject failure to attend a follow-up visit;
- Required assessment/data collection during visit not done;
- Source data permanently lost.

Investigators may not deviate from the CIP, unless the deviation is necessary to protect the rights, safety and wellbeing of the subject in an emergency situation. Deviations should be reported to Medtronic regardless of whether medically justifiable, pre-approved by Medtronic, or taken to protect the subject in emergency. Study deviations should be reported to Medtronic via the study

deviation CRF in a timely manner.

Investigators are also required to adhere to local EC requirements and procedures for reporting study deviations. Reporting of all other study deviations should comply with EC policies and/or local laws and must be reported to Medtronic as soon as possible upon the study site becoming aware of the deviation.

Medtronic is responsible for analyzing deviations, assessing their significance, and identifying any corrective and/or preventive actions that may be warranted. Repetitive or serious investigator compliance issues may represent a need to initiate a corrective action plan, which may include suspension of enrollment or termination of the investigator or site participation in the study.

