The primary analysis will be performed on the Intention To Treat (ITT) set and a sensitivity analysis will be performed using the Per Protocol set including all subjects that were compliant with the protocol.

The ITT includes all patients enrolled in the study those sign Data Release Form, fulfill the inclusion and exclusion criteria. The ITT will be used for all endpoints and safety evaluation. For patients who dropout the analyses will include all data up to the point of their last data collection.

The PP includes all patients enrolled in the study those sign Data Release Form, fulfill the inclusion and exclusion criteria and having at least 70% of time using the Auto Mode. The PP set will be used for all endpoints.

The primary endpoint on efficacy defined as the change of TIR at 6 months from Auto Mode activation at baseline will be analyzed by means of paired (samples) t-test or Wilcoxon signed rank sum test according to the normal or non-normal distribution. The mean change will be displayed together with their 95% confidence interval (95%CI). Additional exploratory analysis on the TIR change over time (baseline, 3, 6 and 12 months follow-up) will be analyzed by means of mixed models for repeated measures. The dependent variable will be pre-log transformed depending on normal or non-normal distribution. The model will have the clinical outcomes as dependent variables and baseline values and visits as explanatory variables. All assumptions for regression models will be performed by assessment of plots of the residual values. Difference between visits means will be tested by applying contrast on the estimated model. The plot for the mean change over time will be

reported.

The secondary endpoint on satisfaction defined by the DTSQc will be analyzed by means of one sample Z- score test. The DTSQc has six items related to treatment satisfaction and two other items assess perceived frequency of hyperglycemia and hypoglycemia. Each item has a maximum of 3 (more satisfied now) and a minimum of -3 (less satisfied now) with a midpoint of 0 reflecting no change. The scale total is computed by adding 6 items (1,4,5,6,7,8) and the 2 items on hypo/hyperglycemia will be analyzed separately. Previous studies on patients treated with MiniMed™ 640G pump have shown a good satisfaction using the DTSQc questionnaire. The sample size estimated would also allow us to demonstrate a positive DTSQc satisfaction score.

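### The severe hypoglycaemia count is tied to an eligibility-restricted ITT set, so any patient treated in deviation from the entry criteria is left out of it (minor)

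*SAP*

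**What the plan says.** SAP 7.1.3 defines the set as follows: "The Intention To Treat (ITT) includes all patients enrolled in the study with signed Data Release Form, fulfill the inclusion and exclusion criteria". The next sentence assigns that set to every endpoint and to safety, so that the condition and the use stand side by side: "fulfill the inclusion and exclusion criteria. The ITT will be used for all endpoints and safety evaluation". Protocol 12.3 has the same definition, "The ITT includes all patients enrolled in the study those sign Data Release Form, fulfill the inclusion and exclusion criteria", and the same use: "The ITT will be used for all endpoints and safety evaluation". The only other set, Per Protocol, is narrower. Neither document defines a safety set or an all-treated set.

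Protocol 10.10 gives, among its examples of deviations, "Subject did not meet enrollment criteria and was enrolled". The first exclusion in Protocol 9.4 is a contraindication in the system's instructions for use.

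On safety data, Protocol 10.8 states: "No Adverse Events or Device Deficiencies are collected, and there are no specific safety parameters to be assessed as part of the study". The synopsis says the same about adverse events. SAP 7.10 nevertheless reports the number of severe hypoglycaemia events with summary statistics and names no analysis set for it. The table in SAP 7.1.3 has a column for adverse events, ticked for ITT only.

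**The concern.** A safety summary should cover everyone exposed to the device. Here, membership depends on having met the entry criteria, which has nothing to do with exposure. A patient who was enrolled and put on the system despite failing a criterion is exposed, but falls outside both defined sets. If that patient has a severe hypoglycaemia event, both the patient and the event are missing from the one safety output the SAP plans.

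The study is meant to describe real-life use in France in support of reimbursement, and its final report goes to the French health authority (Protocol 4.2 and 14.7.4). A reader of that report would expect the count to include patients treated outside the criteria.

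There is also a mismatch in the SAP table: it gives a population for adverse events although the protocol does not collect them.

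**Working it through.** The plan states no figure on this point, so there is nothing to reproduce. The check has two parts: reading the passages together, and an illustration of size.

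**Reading the passages together**

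1. Protocol 9.2 says: "The point of enrollment is defined as the time at which the in- and exclusion criteria have been checked and fulfilled". If that always held, the eligibility condition in the ITT definition would exclude nobody.
2. Protocol 10.10 uses the word enrolled for subjects who did not meet the criteria, so the documents allow for the case.
3. SAP 7.10 names no set, so the rule in SAP 7.1.3 governs the severe hypoglycaemia count. An ineligible patient is therefore not counted.
4. SAP 7.1.2 tabulates and lists all deviations, and SAP 7.1.1 reports numbers enrolled and analysed. The exclusion would be visible, but the excluded patient's events would not be.
5. The adverse events column in SAP 7.1.3 has no data behind it, given Protocol 10.8. In addition, Protocol 10.8 says that no specific safety parameter is assessed, whereas SAP 7.10 reports one.

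**Illustration of size**

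Input from the documents: 306 patients to be enrolled (SAP 6, Protocol 12.2).

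Assumptions, none of them in the documents: 1% to 5% of patients are ineligible (3 to 15 of 306); the risk of at least one severe hypoglycaemia event is 5% in eligible patients; the risk in ineligible patients is either the same or three times as high (15%).

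Formulas, with k ineligible patients at risk r:
- Patients with an event among all treated = (306 − k) × 0.05 + k × r
- Rate among all treated = that number / 306
- Rate in the restricted set = 0.05
- Share of event patients lost = k × r / patients with an event among all treated

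| k | r | Event patients, all treated | Rate, all treated | Rate, restricted set | Understatement | Share of event patients lost |
|---|---|---|---|---|---|---|
| 3 | 5% | 15.15 + 0.15 = 15.3 | 5.0% | 5.0% | 0 | 0.15/15.3 = 1.0% |
| 15 | 5% | 14.55 + 0.75 = 15.3 | 5.0% | 5.0% | 0 | 0.75/15.3 = 4.9% |
| 3 | 15% | 15.15 + 0.45 = 15.6 | 5.1% | 5.0% | 0.1 points | 0.45/15.6 = 2.9% |
| 15 | 15% | 14.55 + 2.25 = 16.8 | 5.5% | 5.0% | 0.5 points | 2.25/16.8 = 13.4% |

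The last column describes the raw count. It does not measure bias in the rate, because the excluded patients leave the denominator as well.

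**The case against.** The strongest reply is that little depends on this. Eligibility is part of the definition of enrolment (Protocol 9.2), so the clause should rarely exclude anyone. Protocol 10.10 is an open list of examples; it shows that the deviation is possible and gives no expected frequency. The study has no safety objective or endpoint. SAP 7.10 plans one descriptive count with no test, and complaint and vigilance reporting runs outside the analysis sets and still covers ineligible patients. All of this stands, and it is why the point is minor. It does not justify the rule: with perfect screening the clause does nothing, and otherwise it removes exposed patients.

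A reader might infer that the excluded patients are those most likely to have events, so that the safety result is materially biased downwards. The documents do not support this. They do not list the contraindications, and several criteria, such as literacy in French or a skin condition at the sensor site, have no evident link to severe hypoglycaemia. The tripled risk above is a scenario only.

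A reader might also infer that the study will issue an empty adverse event table that passes for zero events. SAP 7.10 plans no such table, and the protocol says twice that adverse events are not collected. What stands is an inconsistency between a column heading and the data collection.

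The same clause also removes ineligible patients from the primary time-in-range analysis. That is a separate matter and is not argued here.

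**Conclusion.** The point holds as a matter of definition. As written, a patient treated in deviation from the entry criteria is left out of the only safety summary, and nothing elsewhere in the documents restores that patient. The number affected is unknown and probably small. Under the assumptions shown, the event rate is unchanged at equal risk and understated by about 0.1 to 0.5 percentage points at tripled risk, while the raw count falls in either case. The adverse events column conflicts with Protocol 10.8 whatever the number of ineligible patients, and the passages must be reconciled. No sample-size figure or efficacy result is affected. This is a minor correction, worth making because it costs very little.

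**What to change.** - In SAP 7.1.3 and Protocol 12.3, stop assigning the safety evaluation to the ITT set. Define a safety set of all enrolled patients with evidence of having started the system, whatever their eligibility, and name it in SAP 7.10. The evidence can be a CareLink upload or an Auto Mode activation date. One of these is needed because the case report forms in Protocol 10.2 include no system-start form and Protocol 7.5 provides no device log.
- In SAP 7.10, state the period that the count covers. Include the run-in only if those events are captured. Protocol 10.3 records severe hypoglycaemia at baseline for the previous year, and the synopsis and Protocol 10.4 list it again at 6 and 12 months. Neither says whether run-in events are recorded.
- In the SAP 7.1.3 table, rename the adverse events column to severe hypoglycaemia and note that adverse events are not collected. Align Protocol 10.8 and SAP 7.10 on whether a safety parameter is assessed.

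The cost is a few sentences, one column heading and one more population flag to programme. No new data collection is needed if the count is limited to periods already captured.
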